12.3. Subject Disposition

Subject disposition will be presented by:

- Summary of subjects per visit
- Summary of early withdrawal and reason for early withdrawal.

12.4. Demographics and Baseline Characteristics

Demographics and baseline characteristics of the ITT analysis population will be summarized. These factors will include (but not be limited to):

- Age
- Ethnicity

- Race
- BMI
- Medical history (including diagnosis of SUI)
- Parity
- Smoking status
- Diabetes
- Hysterectomy status
- History of Multiple UTIs

In order to assess if the Altis and Comparator study populations are similar, demographics and baseline characteristics will be compared by t-tests for continuous factors and chi square tests for categorical factors, or non-parametric tests as appropriate. A propensity score analysis will also be performed. If significant differences are found between groups, the impact of relevant factor(s) on success rates will be assessed.

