7.1 Analysis Populations

The Intent-to-Treat (ITT) analysis population consists of all subjects who have undergone a sling implant attempt for stress urinary incontinence for this study using either Altis SIS or a FDA cleared transobturator or retropubic sling. The ITT analysis population is the primary population for the assessment of all safety and effectiveness endpoints.

The per-protocol (PP) population includes all subjects in the ITT analysis population who meet all inclusion/exclusion criteria. The PP population will be used as a secondary (supplementary) analysis population to confirm and further substantiate the results of effectiveness endpoints based on the ITT analysis population.

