This SAP should be read in conjunction with the study protocol and electronic case report forms (eCRF). This version of the plan has been developed with respect to the Altis 522 protocol version 4.0, dated November 01, 2018. Any changes to the protocol or eCRFs may necessitate updates to the SAP. If differences exist between the protocol and the SAP, the SAP shall prevail.

3. Applicable Documents

Document Number	Document Title
Study ID SU020	A Post-Market Evaluation of the Altis Single Incision Sling System versus Transobturator or Retropubic Mesh Sling in the Treatment of Female Stress Urinary Incontinence (Altis 522 Study)

4. Software

All tables, listings and figures will be produced using SAS Version 9.4 (SAS Institute, Cary, NC.) or a later version of SAS. All output will be in Microsoft Word, Microsoft Excel or RTF format. Other reporting software (such as R) may be used for data analysis, summarizations or visualization of data as necessary.

5. Trial Objectives

The purpose of this postmarket study is to compare the safety and effectiveness of the Altis Single Incision Sling (SIS) to an FDA cleared transobturator and/or retropubic mesh sling through 36 months.

The primary safety and effectiveness objectives of this study are:

1. To demonstrate that the rate of device and/or procedure related serious adverse events associated with use of Altis SIS is non-inferior compared to the rate associated with use of transobturator and/or retropubic slings at 36 months.
2. To demonstrate that the rate of effectiveness associated with use of Altis SIS is non-inferior to the rate associated with use of transobturator or retropubic mesh slings for the treatment of stress urinary incontinence at 6 months.

The secondary objectives of this study are:

3. To demonstrate that the rate of device and/or procedure related adverse events defined as organ perforation, bleeding, mesh exposure in the vagina, mesh erosion into the bladder, pelvic pain, infection, de novo dyspareunia, urinary retention, recurrent incontinence, other urinary problems and neuromuscular problems associated with use of Altis SIS is non-inferior compared to the rate associated with use of transobturator and/or retropubic slings at 36 months.
4. To demonstrate that the rate of revision/resurgery associated with use of Altis SIS is non-inferior compared to the rate associated with use of transobturator and/or retropubic slings at 36 months.

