8.1 Randomization

This is not a randomized study.

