12.2. Analysis Populations

A subject is considered enrolled once signed informed consent is obtained. The **Intent-to-Treat (ITT)** analysis population consists of all enrolled subjects, and will be used as the supplementary population to assess the primary effectiveness endpoint results.

The **modified Intent-to-Treat (mITT)** analysis population is a subset of the ITT population, and includes all enrolled subjects who have undergone a sling implant attempt for stress urinary incontinence using either Altis SIS or an FDA cleared transobturator or retropubic sling. The mITT analysis population is the primary analysis population for the assessment of all safety and effectiveness endpoints.

The **Per-Protocol (PP)** population includes all subjects in the mITT analysis population who meet all inclusion/exclusion criteria. The PP population will be used as a secondary (supplementary) analysis population to confirm and further substantiate the results of effectiveness endpoints based on the mITT analysis population. If the Per-Protocol analysis population does not differ from the mITT analysis population, separate analyses will be not presented.

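### SAP 12.4 judges comparability of non-randomised groups by significance tests, in a baseline table specified for ITT; factors outside the propensity list are followed up only if significant

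*SAP*

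**What the plan says.** SAP 8.1 states: "This is not a randomized study". Comparability of the groups therefore has to be shown and, where lacking, adjusted for.

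- **Comparison of groups, SAP 12.4.** "Demographics and baseline characteristics of the ITT analysis population will be summarized". The section names ten factors in an open list. To decide whether the groups are similar it prescribes t-tests, chi-square tests or non-parametric equivalents. It adds, without condition, that a propensity analysis will be done, and ends: "If significant differences are found between groups, the impact of relevant factor(s) on success rates will be assessed".
- **Populations, SAP 12.2.** The ITT "analysis population consists of all enrolled subjects, and will be used as the supplementary population to assess the primary effectiveness endpoint results". For the main analyses, "The mITT analysis population is the primary analysis population for the assessment of all safety and effectiveness endpoints".
- **Protocol 7.1.** Here the ITT "analysis population consists of all subjects who have undergone a sling implant attempt for stress urinary incontinence for this study", which matches the SAP's mITT. SAP section 2 settles the conflict: "If differences exist between the protocol and the SAP, the SAP shall prevail".
- **Propensity analysis, SAP 12.6.3 and Protocol 7.8.** A logistic model for treatment group yields one score per woman, which enters a logistic model for each primary endpoint. The named covariates are age, parity, BMI, smoking, diabetes, hysterectomy and repeated urinary tract infection. The list is open-ended. The analysis is additional to the unadjusted Z-tests in SAP 12.6.1 and 12.6.2, which decide success.

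**The concern.** In a non-randomised comparison, what matters about a baseline factor is how far the groups differ on it and how strongly it predicts outcome. A p-value measures neither. It mixes the size of the difference with the sample size, so a non-significant result at this sample size does not show similarity. If the follow-up of a factor depends on that result, a prognostic imbalance of moderate size can be reported as no difference and taken no further. The follow-up sentence also mentions only success rates, not safety.

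The second issue is where comparability is shown. The table is specified for everyone who consented, but the non-inferiority tests are run in women with an implant attempt. SAP 12.7.5 expects that some enrolled women may have had no attempt, since it lists their adverse events separately. A table that includes them does not describe the groups being compared.

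**Working it through.** **1. The plan's sample size, reproduced.** Non-inferiority on a difference of proportions, one-sided 0.025, power 80%: n = (1.96 + 0.8416)² × [p₁(1−p₁) + p₂(1−p₂)] / margin².

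- Safety (10% in each group, margin 10%): 7.849 × 0.18 / 0.01 = 141.3, so 142. Divided by 0.80 for 20% attrition: 177.5, so 178 (Protocol 7.9.3).
- Effectiveness (75% in each group, margin 15%): 7.849 × 0.375 / 0.0225 = 130.8, so 131. Divided by 0.80: 164.

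Both documents give the design as 178 per group, so 178 is used below. The lower figures 142 and 164 also appear in the documents and are shown for range.

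**2. What the baseline tests can see.** Two-sided 0.05 (SAP 10.4), with differences in SD units.

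- Smallest significant observed difference = 1.96 × √(2/n). At n = 178: 1.96 × 0.106 = 0.208.
- Chance of detecting a true difference d ≈ Φ(d/√(2/n) − 1.96). For d = 0.20 at n = 178: Φ(1.887 − 1.96) = 0.471, so missed 53% of the time.

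| n per arm | smallest significant difference (SD) | missed at 0.15 SD | missed at 0.20 SD | missed at 0.30 SD |
|---|---|---|---|---|
| 142 | 0.233 | 76% | 61% | 29% |
| 164 | 0.216 | 73% | 56% | 23% |
| 178 | 0.208 | 71% | 53% | 19% |

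For binary factors at 178 per arm, 10% against 17% is missed about 51% of the time and 20% against 28% about 58%. To have 80% power at 0.20 SD would take 2 × 7.849 / 0.04 = 392.4, so 393 per arm.

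The tests also err the other way. With ten independent, perfectly balanced factors, the chance of at least one significant result is 1 − 0.95¹⁰ = 0.40.

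**3. Which factors depend on the trigger.** Setting the lists side by side:

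| Factor | Named in SAP 12.4 | Named in SAP 12.6.3 |
|---|---|---|
| Age, parity, BMI, smoking, diabetes, hysterectomy, repeated UTI | yes | yes |
| Race, ethnicity, medical history including SUI diagnosis | yes | no |
| Baseline pad weight, site | no | no |

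Seven of the ten factors named in 12.4 enter the propensity model regardless of significance. Race, ethnicity and medical history reach a between-group assessment only through the trigger, unless added to the model. Baseline pad weight and site are named in neither list, so even the trigger applies to them only if they are added to 12.4. Yet SAP 12.6.1 names both as candidate variables for imputation, and baseline pad weight is the denominator of the primary effectiveness endpoint.

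The adjusted models cover only the primary endpoints. The two powered secondary safety endpoints (SAP 12.7.1 and 12.7.2) have no planned adjustment.

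**4. An illustration of size, on assumed inputs.** Take a binary factor outside the propensity model, with prevalence about 20% to 50%, that changes success by 20 points. The largest non-significant imbalance at 178 per arm is 1.96 × √(2p(1−p)/178), which is 8 to 10 points. The bias is 0.083 × 0.20 to 0.104 × 0.20, or about 0.02. At the non-inferiority boundary (75% against 60%) with 131 to 178 evaluable women per arm, the standard error is √(0.4275/n) = 0.057 to 0.049. A bias of 0.02 in favour of Altis then moves one-sided type I error from 0.025 to Φ(0.02/SE − 1.96) = 0.054 to 0.060. The prevalence and the 20-point effect are assumptions; the documents give neither.

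**The case against.** The strongest reply is that the SAP already has its main safeguard. The sentence just before the trigger promises a propensity analysis with no p-value attached, and SAP 12.6.3 specifies it for both primary endpoints. A reader might infer from 12.4 that only significant factors are ever examined. The documents do not support that: seven factors are adjusted for regardless, and the list may be extended. This stands, and it confines the point to factors outside the list and to endpoints outside the propensity analysis. Baseline pad weight also gets attention elsewhere, in the imputation model and in the subgroups of SAP 12.10, but neither is an adjustment between groups.

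A reader might also infer that ITT is simply the wrong population for the table. That goes too far. SAP 12.2 and 12.6.1 use ITT for a supplementary effectiveness analysis, so an ITT table has a use. The sentence on tests names no population, and the label may be carried over from the protocol's definition. The documents do not say how many consented women had no implant attempt, or how they would be assigned to a group. What remains is that nothing requires comparability to be shown in mITT.

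Finally, the figures for missed imbalances describe the power of a baseline test, not bias in an endpoint. That is correct. The bias in step 4 needs an assumed effect of the factor on outcome, and 0.02 is small against a margin of 0.15. Moreover, success rests on the unadjusted Z-tests, so that bias would be present with or without the trigger. The trigger affects only whether anyone looks for it.

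**Conclusion.** The point holds in a limited form, as a cheap improvement. SAP 12.4 uses significance tests to judge similarity, and at 178 per arm these miss a true 0.20 SD imbalance about 53% of the time (61% at 142 per arm). For the seven named propensity covariates this does little harm to the primary endpoints. For race, ethnicity and SUI diagnosis, a between-group assessment depends on a significant result. For baseline pad weight and site it depends on someone adding them to a list first. The baseline table is specified for a population other than the one in which success is decided.

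The documents do not show that any imbalance exists, that the ITT and mITT populations differ materially, or that the trigger would change the success decision. The type I error of 0.054 to 0.060 is an illustration on assumed inputs, not an estimate for this trial. The detection figures rest on normal approximations and equal arms.

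**What to change.** Amend the SAP as follows.

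1. In 12.4, present and compare baseline characteristics in mITT, keeping the ITT table if wanted.
2. Report standardised differences for every factor, before and after propensity adjustment, as a balance diagnostic.
3. Delete the sentence that makes the assessment of a factor conditional on significance.
4. In 12.6.3, replace the open list with a pre-specified covariate set that adds baseline pad weight, which is already collected, and other prognostic factors such as race, ethnicity, SUI diagnosis and site, whatever their p-values. Sites with few women may need pooling.
5. State whether the powered secondary safety endpoints will have the same adjusted analysis.

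A cut-off such as 0.10 SD is a convention that does not come from the documents, and it should not replace the p-value as the sole trigger. At 178 per arm the standard error of a standardised difference is √(2/178) = 0.106, so 0.10/0.106 = 0.94, and about 35% of perfectly balanced factors would exceed it by chance. The protection should come from the pre-specified covariates.

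The cost is SAP wording, one more table and a slightly larger propensity model. Sample size and data collection do not change.

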12.5. Study Endpoints

12.5.1. Primary Safety Endpoint

- Observed device and/or procedure-related serious adverse events through 36-months.

12.5.2. Primary Effectiveness Endpoint

- Observed effectiveness, defined as a reduction from baseline in 24 hour pad weight of at least 50% at 6 months.

12.5.3. Secondary Safety Endpoints

- Observed rates of device and/or procedure-related adverse events defined as organ perforation, bleeding, mesh exposure in the vagina, mesh erosion into the bladder, pelvic pain, infection, de novo dyspareunia, urinary retention, recurrent incontinence, other urinary problems and neuromuscular problems through 6, 12, 18, 24, and 36 months post index procedure. The rate of events through 36 months will be considered the powered endpoint.
- Observed revision/re-surgery through 6, 12, 18, 24, and 36 months post index procedure. The rate of events through 36 months will be considered the powered endpoint.
- All observed adverse events through 6, 12, 18, 24, and 36 months post index procedure

12.5.4. Secondary Effectiveness Endpoints

- Observed effectiveness defined as a reduction from baseline in 24 hour pad weight of at least 50% at 12, 18, 24, and 36 months.
- Observed effectiveness for subjects considered dry (pad weight \leq 4.0 grams) at 6, 12, 18, 24, and 36 months.
- Quality of Life at 6, 12, 18, 24, and 36 months as measured through:
 - Patient Global Impression of Improvement (PGI-I)
 - Urogenital Distress Inventory (UDI-6)
 - Incontinence Impact Questionnaire-Short Form (IIQ-7)
 - Surgical Satisfaction Questionnaire (SSQ-8)

- Visual Analog Scale for Pain (VAS Pain)

12.6. *Analyses of Primary Endpoints*

12.6.1. *Primary Effectiveness Analyses*

For the purpose of the primary effectiveness analysis, a subject will be considered a success at 6 months if there is a $\geq 50\%$ reduction in pad weight from baseline in the mITT analysis population. A subject with $< 50\%$ reduction in pad weight from baseline will be considered a failure.

Main Analysis

The number and proportion of subjects meeting the primary endpoint will be tabulated for each treatment group at 6 months. Non-inferiority will be assessed using a normal approximation test (Z-test) for a difference in binomial proportion. Non-inferiority will be achieved if the upper limit of the 95% confidence interval for the difference in proportions (Comparator – Altis) is less than 0.15. If non-inferiority is achieved and the upper limit of the 95% confidence interval for difference in proportions (Comparator – Altis) is less than 0, superiority of Altis can also be claimed. As this follows a simple closed test procedure, no multiplicity adjustment is necessary.

The primary analysis of this endpoint will include all available data and ‘presumed failures’ from the mITT analysis population. Presumed failures are defined as subjects with missing data where it is known that the cause of the data loss is either related (1) to an adverse event, including death, or (2) to a device failure. ‘Presumed failures’ will be considered failures for all primary effectiveness endpoint analyses. ‘Presumed failures’ will contribute available data up to the point of failure, and will be considered failures in the primary effectiveness endpoint analysis after the point of failure. Subjects with missing data for other reasons will be ignored in the primary analysis. As described above, the primary effectiveness endpoint will also be summarized for the PP analysis set, following the same logic as the main analysis in the mITT analysis set.

Sensitivity Analyses

The following sensitivity analyses will be performed on the primary effectiveness endpoint:

- An analysis utilizing multiple imputation (MI) for missing values will be performed for the primary effectiveness endpoint based on the mITT analysis population. Selection of variables for the MI analysis will be performed by first assessing the correlation of relevant baseline variables including, but not limited to: baseline age, investigational site, and baseline pad weight. The initial list of candidate variables may be adjusted to allow for proper model convergence. A total of 100 imputed datasets will be created to determine the imputed effect size.
- The primary effectiveness endpoint will also be assessed in the ITT analysis population. Again, multiple imputation method will be employed to impute missing values.
 - A comparison of relevant baseline and clinical variables between missing and non-missing subjects will also be used to assess the likelihood that missingness is differential or non-differential. Non-differential missingness with respect to the outcome is known to not bias results, but to attenuate a

given effect size. Should missing subjects and non-missing subjects demonstrate high concordance on baseline factors, it can be reasonably argued that missingness is non-differential and therefore results from complete case analyses are unbiased.

- Additional sensitivity analyses for the primary effectiveness endpoint will include best case, worst case and tipping point analysis, and will be based on the mITT analysis set.

Subjects who are considered ‘presumed failures’ will still be considered failures in the sensitivity analyses, while outcomes for subjects with missing values for other reasons will be imputed.

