7.4. Revision/Resurgery Hypotheses

The number and proportion of subjects experiencing revision and/or resurgery will be tabulated for each treatment group. Non-inferiority at 36 months will be calculated using a normal approximation test (Z-test) for a difference in binomial proportion with the following null and alternative hypotheses:

$$H_0: \pi_C - \pi_T \leq -0.10$$

$$H_A: \pi_C - \pi_T > -0.10$$

where π_C is the proportion of subjects who have the revision/resurgery endpoint during follow-up in the Comparator group and π_T is the proportion of subjects who have the revision/resurgery endpoint during follow-up in the Altis group and 0.10 is the non-inferiority margin.

7. Trial Success Criteria

The Altis 522 will be evaluated according to the primary effectiveness and safety objectives. The study will be considered a success if both primary objectives (effectiveness and safety) are met.

8. Trial Design

This is a prospective, post-market, multi-center, cohort assessment comparing Altis SIS (n=178) and transobturator and/or retropubic slings (n=178) in the treatment of stress urinary incontinence, at up to 40 U.S. and International sites. Subjects will be followed for a total of 36 months with scheduled visits at 6, 12, 18, 24 and 36 months.

The study population will consist of adult female subjects with stress urinary incontinence who are clinically indicated for surgical intervention with a mesh sling. All study candidates who provide written informed consent and meet all the inclusion criteria and none of the exclusion criteria will be included in the study. Subject enrollment will continue until the required sample size is successfully reached. No site may enroll more than 20% of subjects without prior approval from Coloplast Corp.

Schedule of Procedures:

Data Collection	Baseline	Procedure	6 Month	12 Month	18 Month	24 Month	36 Month	Un-scheduled ⁴
Informed Consent Obtained	X							
Inclusion/Exclusion Criteria Verified	X							
Pregnancy Test	X ¹							
Urinalysis	X ²							
Medical History	X							
Procedural Data		X						
Cystoscopy		X						
Post Void Residual Test	X ³		X	X	X	X	X	
Cough Stress Test	X ³		X	X	X	X	X	
24-Hour Pad Weight Test	X ³		X ⁵					
Medication Documentation	X	X	X	X	X	X	X	

Data Collection	Baseline	Procedure	6 Month	12 Month	18 Month	24 Month	36 Month	Un-scheduled ⁴
Patient Global Impression of Improvement (PGI-I)			X	X	X	X	X	
Surgical Satisfaction Questionnaire (SSQ-8)			X					

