10.3. Sample Size Estimation for Powered Secondary Safety Endpoints

The total sample size required to meet the primary safety and effectiveness objectives is 262 subjects not accounting for attrition. The overall rate of device or procedure related adverse events in the IDE study is 14%. A conservative estimate of 20% is chosen to account for the additional follow-up time. Assuming an underlying rate of any device and/or procedure related adverse event of 20% in each group, a sample size of 112 per study group, for a total of 224 subjects is required to power for the assessment of the secondary safety endpoint.

Because the rates of revision/resurgery are expected to be less than the rates for the primary safety endpoint, the study is adequately powered for this objective as this endpoint utilizes the same non-inferiority margin as the primary safety endpoint.

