10.4. Level of Significance and Power

All tests of significance will be performed at the two-sided 0.05 significance level (one-sided 0.025), unless otherwise specified. As both the primary effectiveness and safety objectives must be met for study success, no adjustment for multiplicity is required. Additionally, the powered secondary safety endpoints for (1) device and/or procedure related adverse events, and (2) revision or resurgery will be tested hierarchically in the order presented in the event the primary safety objective is met. Therefore, no adjustment for multiplicity is required.

10. Data Structure and Handling

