13.5 Visual Analog Scale (VAS)

The VAS will be completed by the subject at baseline and at 6 months following the index procedure. In addition, the subject will complete a VAS Pain questionnaire each day for the 3

days following their index procedure. The subject will be supplied with a postage paid return envelope to send the questionnaires back to the study site upon completion.

13. Validation

Validation of statistical programs will be performed for any analyses sent to the FDA, provided for publication or as requested by Coloplast. Validation level required will be specified by Coloplast.

14. Version History

Version	Date	Changes
1.0	07 SEP 2017	Initial version.
2.0	01 NOV 2018	
Revised power analysis to account for equal allocation.Clarified analysis populations.Added subgroup analyses.
3.0	21 MAR 2021	
Updated analysis populations.Detailed additional sensitivity analyses for the primary effectiveness endpoint, including details of imputations.Added analysis for 1.3 gram cutoff for proportion of dry.Elaborated on exploratory analyses.
4.0	08 AUG 2021	
Added details on analyses of secondary endpoints.Replaced treatment group with 'Altis' and control group with 'Comparator'.Added document approval section.Added superiority testing if non-inferiority is achieved.Revised section 12.7.3 (24-Hour Pad Weight) to distinguish between endpoints and associated analyses.

15. References

NA

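### SAP 12.6 and 12.7 allow superiority claims on four endpoints at one-sided 0.025 each, and no rule controls those claims across endpoints

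*SAP*

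**What the plan says.** SAP 12.6.1 (effectiveness at 6 months), 12.6.2 (related serious adverse events through 36 months), 12.7.1 (related adverse events) and 12.7.2 (revision/resurgery) share one structure. Non-inferiority is judged by the 95% confidence interval against the margin. If it is achieved and the interval also lies wholly on Altis's side of zero, "superiority of Altis can also be claimed". Each section then says: "As this follows a simple closed test procedure, no multiplicity adjustment is necessary".

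SAP 10.4 sets the level at two-sided 0.05 (one-sided 0.025) and gives two reasons for not adjusting:
- For the primaries: "As both the primary effectiveness and safety objectives must be met for study success, no adjustment for multiplicity is required".
- The two powered secondaries "will be tested hierarchically in the order presented in the event the primary safety objective is met".

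SAP 10.4 does not mention superiority. Superiority is also absent from the SAP's objectives and hypotheses and from Protocol 7.4 to 7.6. The SAP version history lists it under version 4.0: "Added superiority testing if non-inferiority is achieved". No multiplicity rule is listed beside it. The success criterion in SAP 7 is: "The study will be considered a success if both primary objectives (effectiveness and safety) are met".

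**The concern.** The closed-test argument protects one endpoint at a time. A superiority claim on an endpoint needs only that endpoint's interval to exclude zero, so four endpoints give four chances of a false claim, all in favour of Altis.

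Neither argument in SAP 10.4 closes this:
- Requiring both primaries protects the joint non-inferiority conclusion. A superiority claim does not need both, and 12.6.1 does not make the effectiveness claim depend on safety.
- The secondary order is opened by the primary safety objective, which is non-inferiority. The text does not say whether the order also applies to the secondary superiority tests, and it does not rank the two primary superiority claims.

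If superiority on any one of the four is reported as a finding of the study, a reader of the SAP would take the error rate to be already controlled. It is controlled per claim, not across the claims.

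**Working it through.** **Inputs from the documents.** Level one-sided 0.025 (SAP 10.4). Effectiveness 75% in both arms, margin 15%, 131 evaluable per arm (SAP 10.1). Related serious adverse events (SAE) 10% in both arms, margin 10%, 142 per arm (SAP 10.2). Related adverse events (AE) 20% in both arms, margin 15%, 112 per arm (SAP 10.3). Planned size 178 per arm (SAP 8). For revision/resurgery the SAP gives no figure, only this: "Because the rates of revision/resurgery are expected to be less than the rates for the primary safety endpoint".

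**The plan's own figures.** n = (1.960 + 0.842)² × 2p(1−p) / margin², with (1.960 + 0.842)² ≈ 7.849:
- Effectiveness: 7.849 × 0.375 / 0.0225 = 130.8, so 131.
- SAE: 7.849 × 0.18 / 0.01 = 141.3, so 142.
- AE: 7.849 × 0.32 / 0.0225 = 111.6, so 112.

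All three agree, so the unpooled normal approximation at one-sided 0.025 is the right model of the plan's tests.

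**Two primaries.** Safety uses 178 per arm. Effectiveness uses 178 × 0.8 ≈ 142 evaluable. True rates are equal, the intervals are unpooled 95%, the binomial enumeration is exact, and effectiveness is taken as independent of safety.
- False superiority on effectiveness: 0.0255. On SAE: 0.0262.
- Either: 1 − (1 − 0.0255)(1 − 0.0262) = 0.0510. The nominal version is 1 − 0.975² = 0.0494.
- With both primary non-inferiority objectives also required (pass probabilities 0.834 for effectiveness and 0.882 for safety): 0.0255 × 0.882 + 0.0262 × 0.834 − 0.0255 × 0.0262 = 0.0436.
- With 131 evaluable, either: 0.0518. With the SAE rate at the earlier IDE study's 2.7%: 0.0475.
- If effectiveness is lower after an adverse event (assumed 45% after an SAE, 65% after another AE), either: 0.049.

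None of these needs a revision rate.

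**All four.** 400,000 simulated trials per scenario at the planning rates. SAEs are counted within AEs. Secondary claims are allowed only after primary safety non-inferiority and in the 10.4 non-inferiority order. The revision rate and its overlap are assumed.

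| Assumed revision/resurgery | At least one false claim, 10.4 order binding non-inferiority only |
|---|---|
| 3%, all within SAEs | 8.6% |
| 9%, all within SAEs | 7.6% |
| 5%, half SAE, half other AE | 8.7% |
| 8%, half SAE, half other AE | 8.6% |
| 8%, mostly outside AEs | 8.9% |

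If the 10.4 order also binds secondary superiority (revision claimed only after AE superiority), the figure is about 6.9% in every row. The revision assumption then hardly matters, because a false revision claim can only follow a false AE claim.

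**A fixed order.** A false claim can arise only if the first endpoint in the order that has no true advantage is falsely declared superior. Each single test errs at 2.2% to 2.6% in the scenarios run, so the chance of any false claim stays near 2.5%. With all endpoints equal and primary safety first it is 2.6%, the size of that first normal-approximation test.

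**The case against.** The strongest reply is that no study decision rests on these claims. Success is non-inferiority on both primaries. Superiority is optional, prespecified and open only after non-inferiority on the same endpoint. Each claim read alone keeps its level, and the quoted sentence is true of the step it follows. Pad weight at 6 months and serious events through 36 months are different questions, so whether they must share one 2.5% is partly a judgement. The documents do not state what use the claims are meant for.

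Most of this stands, and it limits the weight of the point. It does not remove the gap. The SAP speaks of claims rather than description, says without qualification that no adjustment is needed, and leaves 10.4, the section that handles multiplicity, silent on superiority.

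A reader might go further in three ways that the documents do not support:
- That non-inferiority or study success is inflated. Both primaries must pass, and the secondary non-inferiority tests are ordered.
- That the four-claim figure is simply 1 − 0.975⁴ = 9.6%. That ignores the ordering in 10.4 and the overlap between serious events, related events and revisions.
- That confounding belongs in this calculation. SAP 8.1 says "This is not a randomized study", but case-mix differences are bias, which no multiplicity rule repairs. SAP 12.6.3 plans a propensity analysis for that.

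**Conclusion.** The point holds for superiority claims taken across endpoints. With truly equal, comparable arms at the planning rates, the chance of at least one false claim is about 5.1% for the two primaries, or about 4.4% if both primary objectives must also be met. The benchmark is one-sided 2.5%, because every counted claim favours Altis.

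For all four endpoints the size depends on how 10.4 is read: about 6.9% if its order also binds the secondary superiority tests, and roughly 7.5% to 9% if it binds only non-inferiority. The second range rests on assumed revision rates and overlaps. Both four-claim figures assume effectiveness independent of safety. That is not strictly so, since 12.6.1 counts pad-weight data lost because of an adverse event as failure; the correlated run for the primaries suggests a small effect. None of these figures is a strict bound. The pad-weight change tests in 12.7.3 are not counted, because no claim is attached to them.

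**What to change.** Add one rule to SAP 10.4, refer to it from 12.6.1, 12.6.2, 12.7.1 and 12.7.2, and limit the no-adjustment sentence there to the step within an endpoint. Either rule would do:

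- **(A)** Superiority results are reported descriptively, unadjusted across endpoints, and support no superiority claim.
- **(B)** Superiority is tested at one-sided 0.025 in one fixed, prespecified order (for example primary safety, primary effectiveness, related adverse events, revision/resurgery). Each test follows only after non-inferiority on that endpoint under 10.4. Testing stops at the first failure, and later results are descriptive.

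Under B, no further condition that both primaries be met is needed to hold the chance of any false superiority claim near 2.5%. Adding one would cost power. If SAE rates were truly 10% versus 2% and effectiveness equal, the chance of an SAE superiority claim would fall from 92% to 0.920 × 0.834 = 77%.

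The cost is one SAP version with a version-history entry. No protocol change is needed, since Protocol 7.4 to 7.6 contain no superiority test, and no data or subjects are added. The downside is fewer optional claims. Under A there are none, and under B an endpoint late in the order can be claimed only if the earlier ones succeed, so the order should reflect which claims matter most.
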